ID: IB2019-METABONE

Patterns of Care and Outcomes in Patients With Metastatic Bone Tumors (METABONE)

NCT03963531

Jan 5, 2007

INCLUSION

- Patients age > 12 year old at initial diagnosis
- Histology of Ewing's sarcoma type, osteosarcoma, chondrosarcoma
- Diagnostic of primary event between 2008 and 2018
- Diagnostic of unresectable locoregional disease where palliative treatment is indicated, or metastatic disease
- Treatment and monitoring made in one of the GSF-GETO centers, with follow up data on treatment received available.

OBJECTIFS

I. OBJECTIVES AND ENDPOINTS

The primary objective of the METABONE study is to give a retrospective descriptive analysis of clinico-biological profiles, patterns of care and modalities of treatment of patients with unresectable locally advanced and/or metastatic malignant bone tumors in a real-life national setting.

The primary endpoint is description of initial and local/metastatic relapse events management of adult patients with the diagnosis of Ewing's sarcoma, osteosarcoma, chondrosarcoma, made in one of the centers of the RESOS network between 2008 and 2018, in terms of therapeutic strategies including chemotherapy, surgery, radiotherapy, interventional radiology.

Secondary endpoints

- Description of systemic treatments received in the palliative setting in terms of **PFS** (progression free survival) and **TNT** (Time to next treatment)
- **Overall survival** from unresectable locally advanced and/or metastatic stage
- Identification of **factors associated with PFS and TNT** for molecules used in the unresectable locally advanced and metastatic setting
- Identification of **prognostic factors for overall survival** (OS) in the unresectable locally advanced and/ metastatic setting

II. METHODS

PATIENTS

We estimate the population size in the database of about 2800 patient cases.

We seek to include 800 patients to be screened in the present study.

We aim to get about 400 to 500 informative patients with unresectable locally advanced or metastatic disease.

VARIABLES

Variables collected will be those of the **CONTICABONE DICTIONNARY**

Descriptive data

Centers, number of patients per center

Initial patients characteristics at diagnostic: Age at diagnosis, gender, PS at diagnosis, previous history of specific disease (Li Fraumeni, Multiple Exostosis)

Tumor characteristics at diagnostic : location, side, size, multifocality, LR spread and type, stage N M, histology, grade, previous radiation area,

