Initial treatment: surgery, type of surgery, margins, tumor spillage, residual cellularity, neo/adjuvant systemic treatment indication (start and stop date, type), radiation therapy, other treatment (cryotherapy, radiofrequency, embolisation), clinical trial inclusion

Metastatic relapse/event characteristics: PS, location of first metastasis, number of sites

Treatment of metastatic event: systemic treatment (PS molecule used, start and stop date, best RECIST response, date of progression, clinical trial), locoregional treatment (surgery, radiotherapy, cryotherapy, radiofrequency, embolisation), clinical trial.

Dates: Birth, initial diagnostic, surgery of primary, local relapse, metastatic relapse, start of each chemo line, date of progression for each chemo line, last contact, death

Samples: Molecular cytogenetics : method (RT PCR, FISH), transcript (FOR EWING SARCOMA ONLY)

Survival data

Median follow up

Progression free survival (PFS): PFS defined as the time from the systemic treatment onset to progression or death due to any cause, whichever comes first. When neither death nor progression is observed, PFS is censored at the date of last patient contact.

Time to next treatment (TNT): TNT defined as the time from the systemic treatment onset to the next treatment or death due to any cause, whichever comes first. When neither death nor new systemic therapy is observed, TNT is censored at the date of last patient contact.

Overall survival (OS): OS is defined as the interval between the diagnosis of first tumor event and the time of death. OS in the unresectable locally advanced setting is defined as the interval between the diagnosis of unresectable locally advanced setting (at diagnosis or relapse) and the time of death. OS in the metastatic setting is defined as the interval between the diagnosis of metastatic disease (at diagnosis or relapse) and the time of death. When death is not observed, OS is censored at the date of last patient contact.

STATISTICS

Statistical analysis of the baseline demographics and clinical outcomes will be based on all data available up to the cut-off date of August 31, 2021.

Descriptive statistics will be used to show the distribution of variables in the population.

The variables included in the univariate and multivariate analyses are the descriptive data including:

- type of chemotherapy used (poly vs mono, class of chemo: TKI, Ifosfamide, other)
- locoregional treatment of metastasis,

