- inclusion in a clinical trial in first line,
- at least one inclusion in a clinical trial during metastatic stage,
- use of off-label drug at least once during metastatic stage

Multivariate logistic regression models will be used to identify biological and clinical factors associated with the type of treatment received after 1st line: in second, third, 4th line, and with the probability of survival 5 years after the diagnosis of metastases.

Follow-up times will be described as median values based on the inverse Kaplan–Meier estimator.

Prognostic factors of TNT for each line (1st, second, Third) and OS will be identified using Cox proportional hazard models.

The correlation between TNT and OS will be evaluated at each of the four first-lines of metastatic chemotherapy by a Spearman rank correlation coefficient and expressed as a value between 0 (no association) and 1 (perfect association). We will use a reviewed copula-based approach that introduces an iterative multiple imputation method for the estimation of the correlation coefficient. The data will be analyzed using the SAS v9.3 and R v3.3 software packages.

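### OS in the unresectable setting is not tied to the palliative condition that governs entry, so on a literal reading some patients bring guaranteed survival time into it

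*Combined protocol and SAP*

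**What the plan says.** All references are to the combined protocol and SAP.

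- **INCLUSION.** The disease-stage criterion is "Diagnostic of unresectable locoregional disease where palliative treatment is indicated, or metastatic disease". The unresectable route therefore has two conditions, and metastatic disease is the alternative route.
- **II. METHODS, Survival data.** OS in the unresectable locally advanced setting is the "interval between the diagnosis of unresectable locally advanced setting (at diagnosis or relapse") and death. Metastatic-setting OS has its own origin, the diagnosis of metastatic disease. The censoring rule is "When death is not observed, OS is censored at the date of last patient contact".
- **I. OBJECTIVES AND ENDPOINTS, Secondary endpoints.** OS is to be reported "from unresectable locally advanced and/or metastatic stage".
- **II. METHODS, Variables, Dates.** The dates to be collected are "Birth, initial diagnostic, surgery of primary, local relapse, metastatic relapse, start of each chemo line, date of progression for each chemo line, last contact, death". Neither a date of unresectability nor a date of palliative indication is listed.
- **STATISTICS.** Prognostic factors for TNT by line "and OS will be identified using Cox proportional hazard models". No delayed entry, left truncation or landmark is described.

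**The concern.** The entry condition and the time origin agree only for patients who are palliative from the day unresectability is diagnosed. The inclusion criterion attaches a palliative qualifier to unresectable disease, and that qualifier has a purpose only if some unresectable disease is not palliative. The protocol's own wording therefore allows for patients in whom the two dates differ.

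Such a patient joins the cohort only by surviving until treatment becomes palliative or metastases appear. If OS is counted from the earlier unresectable diagnosis, the time in between contains no deaths by construction. The resulting curve overstates survival in palliative unresectable disease, the population that the inclusion criterion describes. It does not describe all unresectable disease either, because patients whose disease was controlled, and those who died before a palliative indication, never enter.

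The same interval could affect the prognostic models. Characteristics associated with having had an earlier non-palliative phase would mark patients who carry guaranteed time, and so could look protective.

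**Working it through.** **Step 1. Set the two rules side by side.** The plan gives no OS, event or power figure on this point, so there is nothing of its own to reproduce. The first check is textual.

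| Patient's course | Entry condition first met | OS origin, read literally | Guaranteed time |
|---|---|---|---|
| Unresectable and palliative at diagnosis | Diagnosis | Diagnosis | None |
| Resected first, unresectable and palliative at relapse | Relapse | Relapse | None |
| Unresectable at diagnosis, palliative later | Later date | Diagnosis | The gap |
| Unresectable at diagnosis, qualifies only by metastases | Metastatic diagnosis | Diagnosis, if counted in unresectable-setting OS | The gap |

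The problem is confined to the last two rows. The date list does not resolve them: for disease unresectable at presentation, the natural listed anchor is the initial diagnosis. Long gaps are possible. Primary diagnoses run from 2008 to 2018 and the data cut-off is 31 August 2021, so time from diagnosis to cut-off is about 2.7 to 13.7 years.

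**Step 2. Illustrate the size.** Every input here is an assumption.

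- Survival from the qualifying date is exponential with median 12 months, so λ = ln 2 / 12.
- A share p of patients has an earlier phase, with an exponential delay of median 12 months.
- Survival after the qualifying date is the same with or without an earlier phase.

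For delayed patients, the sum of two exponential times with the same rate has survival exp(−λt)(1 + λt). Mixing with the rest gives

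S(t) = (1 − p)·exp(−λt) + p·exp(−λt)(1 + λt) = exp(−λt)(1 + pλt).

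At t = 12, exp(−λt) = 0.5 and λt = 0.693, so S(12) = 0.5(1 + 0.693p). The median solves S(t) = 0.5.

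| p | 12-month OS (true value 50%) | Median OS (true value 12 months) |
|---|---|---|
| 10% | 0.5 × 1.0693 = 53% | 13.3 months |
| 20% | 0.5 × 1.1386 = 57% | 14.7 months |
| 40% | 0.5 × 1.2773 = 64% | 18.0 months |

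Varying the true median over 9 to 18 months and the median delay over 6 to 18 months, with the same shares, lengthens the median by about 0.8 to 9 months.

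**Step 3. Repeat with a fixed gap.** Let a share s have a fixed gap g. Then S(t) = (1 − s)·exp(−λt) + s·[1 if t < g, otherwise exp(−λ(t − g))].

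| s, g | Apparent median, true 12 months | Apparent median, true 18 months |
|---|---|---|
| 10%, 6 months | 12.7 | 18.7 |
| 20%, 12 months | 15.2 | 20.9 |
| 30%, 24 months | 21.7 | 27.8 |

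If s = 0 or g = 0, there is no shift.

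**Step 4. Compare with sampling error.** The plan gives 400 to 500 informative patients over both routes and no split. Assuming 50 to 100 in the unresectable setting, the standard error of a 50% 12-month OS is √(0.5 × 0.5 / 50) = 7.1 points, or √(0.5 × 0.5 / 100) = 5.0 points. The Step 2 excess of 3.5 to 13.9 points is then between 3.5 / 7.1 = 0.5 and 13.9 / 5.0 = 2.8 standard errors.

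**The case against.** The strongest reply is that the OS sentence refers to a setting, and the setting is already defined by the inclusion criterion. The secondary endpoints support this. PFS and TNT are introduced as a "Description of systemic treatments received in the palliative setting in terms of" those endpoints, and the factors for the same endpoints are then sought "for molecules used in the unresectable locally advanced and metastatic setting". The two terms look interchangeable. On that reading, origin and entry coincide and there is no guaranteed time. This stands as a possible reading, but the OS definition does not state it. A retrospective multicenter dataset with no listed date for either condition needs an explicit rule.

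It is also fair that the documents never mention non-palliative treatment of unresectable disease, that most courses are handled correctly, and that the number affected may be small or zero. The calculations show what follows from assumed shares and delays; they are not evidence that such patients exist in number. At the low end the shift is within sampling noise.

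A reader might infer three stronger things that the documents do not support:

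- That the plan starts OS at any unresectable diagnosis whatever the intent of treatment. It does not say so; that is an inference from the missing qualifier.
- That prognostic factors will be distorted. This was not simulated, and the STATISTICS section does not say which OS definition the Cox models use. Only a possible effect can be claimed.
- That survival from unresectable diagnosis in general is biased upward. Both well-controlled patients and early deaths are missing from that population, so the net direction there is not fixed.

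**Conclusion.** The point holds conditionally and should be settled before analysis. The palliative condition is in the entry criterion and absent from the OS origin, the listed dates do not supply it, and no delayed entry is planned. On the literal reading, patients who were unresectable at diagnosis and qualified later contribute guaranteed survival time. On the reading in which the setting already means the palliative state, they do not.

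Under the literal reading the direction is clear for palliative unresectable disease: adding non-negative time to the same patients can only lengthen their OS. The size depends on the share and delay of such patients, which the documents do not give. A 12-month median becoming 13.3 to 18.0 months rests on an assumed share of 10% to 40%, a 12-month median delay, exponential times, and equal survival after qualification in both groups. For patients who qualify only through metastases, the effect also depends on whether they are counted in unresectable-setting OS, which the plan leaves open.

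**What to change.** In II. METHODS, Survival data, define time zero for OS in the unresectable locally advanced setting as the first date on which the inclusion condition is met, that is, unresectable locoregional disease with palliative treatment indicated. State one rule for deriving that date from those already collected (initial diagnosis, local relapse, progression or line start), and fix it before survival is examined. If the sponsor already means the qualifying state, this simply records it.

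An alternative is to keep the earlier origin and enter each patient into the risk set only at the qualifying date (delayed entry). This removes the guaranteed time but does not recover patients whose disease was controlled and who never qualified, so the first option fits the stated population better.

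Under either option, count patients who qualify only through metastases in metastatic-setting OS only, state which OS the Cox models use, and report how many patients have an unresectable diagnosis before their qualifying date.

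**Cost.** A short definition and one derived date. For some patients the date must be inferred, and those with no systemic line have no line-start date to use, so the rule needs a stated fallback. The reported OS may be somewhat shorter.

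### The covariate rule for the TNT and OS models is not limited to variables known when the clock starts; it admits same-line best response and explicitly lists two 'ever during the metastatic stage' covariates

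*Combined protocol and SAP*

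**What the plan says.** The Statistics section sets the covariates for all modelling in one sentence, "The variables included in the univariate and multivariate analyses are the descriptive data including", followed by five items. Two of the five are "at least one inclusion in a clinical trial during metastatic stage" and "use of off-label drug at least once during metastatic stage".

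Under Methods, Variables, the block headed as descriptive data runs until the survival definitions begin. For each systemic line it holds "best RECIST response, date of progression, clinical trial". For initial treatment it holds "surgery, type of surgery, margins, tumor spillage, residual cellularity". For samples it holds "transcript (FOR EWING SARCOMA ONLY").

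The time origins are defined in the survival part: "TNT defined as the time from the systemic treatment onset to the next treatment or death due to any cause". OS in the metastatic setting runs from the diagnosis of metastatic disease. Cox models are planned for TNT in each of the first three lines and for OS. The plan states no restriction by time origin, no landmark or time-dependent handling, no rule for selecting covariates, no rule for missing covariates and no histology-specific models. The only imputation mentioned belongs to the TNT-OS correlation.

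**The concern.** A Cox model with a fixed covariate treats its value as known at time zero. Best response to a line is known only later, and only for a patient who stayed event-free long enough to be assessed. Joining a trial or receiving an off-label drug at some point in the metastatic stage likewise requires being alive when it happens. Patients who die early fall into the 'no' group by construction. The event-free time before the attribute was acquired is then credited to the 'yes' group, and the hazard ratio drops below 1 with no effect present.

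At stake are two stated secondary endpoints: factors associated with PFS and TNT, and prognostic factors for OS. A spurious protective association with trial participation, off-label treatment or response could be reported as a finding, and it can distort the coefficients of the other factors in the same model.

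A second, lesser question is what happens to variables that do not exist for every patient. Transcript applies to one of three histologies. Margins, spillage and residual cellularity presuppose surgery, in a cohort that admits unresectable disease.

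**Working it through.** **No figure to reproduce.** The plan gives no power, event or effect-size calculation. Its 400 to 500 informative patients (Methods, Patients) is a feasibility target. The simulations use the midpoint, n=450.

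**Mechanism, by hand.** Assume exponential TNT with a median of 4 months, response scored at 2 months, and 30% of those still event-free counted as responders.
- Event-free at 2 months: 0.5^(2/4) = 0.707.
- Responders: 0.30 × 0.707 = 0.212 of all patients, with no events before month 2.
- Events before month 2: 1 − 0.707 = 0.293 of all patients, every one scored a non-responder.

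After month 2 the two groups have the same hazard. The whole apparent benefit comes from the first two months.

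**Null simulations.** The true hazard ratio is 1, with exponential event times, censoring uniform over 24 to 120 months, 100 data sets per setting, and the attribute entered as a fixed covariate. The documents supply none of the medians, rates or timings; all are assumptions.
- Set-up A: 40% potential responders, scored at 2, 4 or 6 months (50/30/20%) if still event-free.
- Set-up B: 30% scored at 2 months if still event-free.
- 'Ever' covariate: waiting time with a median of 24 months, independent of prognosis, counted if reached before death or censoring.

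| Covariate | Outcome, medians (months) | Mean HR | p<0.05 |
|---|---|---|---|
| Same-line response, A | TNT 4, 6, 8 | 0.54, 0.62, 0.68 | 100%, 100%, 96% |
| Same-line response, B | TNT 3, 4, 6 | 0.61, 0.68, 0.76 | 100%, 94%, 69% |
| Same-line response, A | OS 12 to 24 | about 0.76 to 0.83 | not tabulated |
| Same-line response, B | OS 12, 18, 24 | 0.87, 0.89, 0.90 | 28%, 21%, 12% |
| 'Ever' covariate | OS 12, 18, 24 | 0.37, 0.34, 0.31 | 100%, 100%, 100% |

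Repeat runs move the OS response figures by a few hundredths. The 'ever' bias is far larger because the waiting time is long relative to survival.

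**Variables not defined for everyone.** If transcript and the surgical variables entered one pooled model and incomplete rows were deleted, the share kept would be Ewing share × operated share × share with known transcript, treating the three as independent. With assumed shares of 25-45%, 40-70% and 70-90%:
- Low: 0.25 × 0.40 × 0.70 = 0.070, and 0.070 × 400 = 28 patients.
- High: 0.45 × 0.70 × 0.90 = 0.284, and 0.2835 × 500 = 142 patients.

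**The case against.** The strongest reply is that the sentence cannot be taken literally. The same descriptive block contains patient counts per center and the dates of progression, last contact and death, which nobody would enter as covariates. It reads better as a loose description of a candidate pool, and best response, transcript and the surgical variables are in none of the five bullets. This stands in part: a reader might infer that every descriptive variable will be put into every model, and the documents do not support that. But the list is introduced as non-exhaustive, and it names no age, performance status, histology or stage, so any usable prognostic model must draw on the block. The reply also does not touch the two 'ever' covariates, which are named outright.

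A second reply is that response is not always a post-baseline variable. Response to an earlier line is known when the second or third line starts and is a legitimate covariate there. This stands, so the problem is confined to response in the line being analysed.

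A third reply concerns size. The response figures depend on assumed rates and timings, and the OS bias from response is modest. This also stands, and calling response a strong spurious factor for OS would go too far.

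Finally, a reader might infer that the models will lose most of their patients. That needs a pooled model, joint entry of transcript and surgical variables, and complete-case deletion. The plan neither states nor excludes these. It gives no histology or surgery shares, and the data dictionary it relies on may already code not applicable. Patients with metastatic relapse may often have had their primary resected. The loss is a possibility, not a result.

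**Conclusion.** The time-origin defect holds. The rule admits covariates fixed by later events and names two of them, and nothing in the plan prevents their use as baseline values. Under the stated assumptions and with no true effect, same-line response would show a TNT hazard ratio of about 0.54-0.76 (medians 3-8 months) and an OS hazard ratio of about 0.76-0.90 (medians 12-24 months). An 'ever' covariate would show an OS hazard ratio of about 0.31-0.37. The direction follows from the design of the covariate; the size depends on assumed medians, response rates and waiting times. The 'ever' covariates were quantified for OS only.

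The bias is conditional on fixed-covariate use, which the plan leaves open. On variables limited to Ewing sarcoma or operated patients, the supported statement is only that their handling is not specified; the 7-28% retention is illustrative. The primary objective is descriptive and is unaffected. The secondary prognostic analyses should be corrected before they are run.

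**What to change.** Replace the covariate sentence with: *Models include only descriptive variables known at the time origin of the model and defined for all patients in it.* Then add:

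- Same-line best response, ever trial inclusion and ever off-label use enter only as time-dependent covariates, or in a landmark analysis with the landmark fixed in advance. Response to an earlier line may be used in models for later lines.
- Transcript is used only in Ewing models.
- Surgical variables carry a 'not operated' level, or are used only in operated patients.

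The cost is mainly wording. The line start dates, molecule and trial status by line are already listed for collection, so trial inclusion and off-label use can be dated by the line in which they occur. No date of response is among the listed variables. If the data dictionary has none, same-line response should be left out of these models.

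A landmark analysis drops patients with an event before the landmark. For a 2-month landmark under exponential TNT the share is 1 − 0.5^(2/median): 37% at a median of 3 months, 29% at 4 and 16% at 8. Its results apply only to patients still event-free at that point.

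### The two trial-participation covariates overlap and one is ever/never, so the joint first-line estimate for OS is not against no trial and carries immortal-time bias

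*Combined protocol and SAP*

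**What the plan says.** The Statistics section of the combined protocol and SAP introduces its covariates with "The variables included in the univariate and multivariate analyses are the descriptive data including", followed by a list. Two separate items on that list are "inclusion in a clinical trial in first line" and "at least one inclusion in a clinical trial during metastatic stage". The plan gives no joint coding, reference group, selection rule or time-dependent handling for them.

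First line is not defined in the list. Elsewhere in the section, lines are lines of treatment for metastatic disease ("at each of the four first-lines of metastatic chemotherapy"). Trial inclusion during initial treatment is recorded as its own field under Variables.

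The list serves several models:
- Cox models: "Prognostic factors of TNT for each line (1st, second, Third) and OS will be identified using Cox proportional hazard models".
- Logistic models for treatment after first line and for being alive 5 years after the diagnosis of metastases.

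Under Survival data, "OS in the metastatic setting is defined as the interval between the diagnosis of metastatic disease (at diagnosis or relapse) and the time of death". The inclusion criteria also admit patients without metastases: "Diagnostic of unresectable locoregional disease where palliative treatment is indicated, or metastatic disease".

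**The concern.** There are two distinct problems.

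**Nesting.** If first line is the first metastatic line, nobody with metastatic disease can have a first-line trial without also having at least one trial in the metastatic stage. With both indicators in one model, the first-line coefficient no longer has no trial as its reference. A reader of the coefficient table would take it as the association of first-line trial inclusion with OS, which it is not.

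**Immortal time.** The clock for metastatic OS starts at metastatic diagnosis, but a trial at a later line can only be entered by someone still alive at that line. Coded ever/never, the later-trial group is credited with survival that it had to have in order to be classified. That group then looks favourable, and a first-line coefficient measured against it is pushed upward.

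Prognostic factors for OS are a stated secondary endpoint. The published result could show no association, or harm, for first-line trial inclusion purely because of coding.

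**Working it through.** The plan gives no participation rate, survival figure or effect size, so it has no figure of its own to reproduce. The only input from the documents is the target of 400 to 500 informative patients. Everything else numerical below is an assumption.

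**Step 1: what the joint coefficient means.** Let F = trial at first metastatic line and A = any metastatic-stage trial, with log hazard bF·F + bA·A.
- No trial: 0
- Later-line trial only: bA
- First-line trial: bF + bA

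So exp(bF) = HR(first-line vs none) ÷ HR(later-only vs none). The first-line versus none contrast is exp(bF + bA).

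**Step 2: nesting alone.** Simulation: 450 patients, 400 replicates, median OS 18 months, 15% in a first-line trial, 20% later-trial probability among the rest, censoring uniform over 32 to 120 months. Later status is fixed at baseline, so there is no immortal time. The true first-line HR versus none is 0.70.

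| True later-only HR | Algebra | Simulated joint first-line HR | Three-level, first-line vs none |
|---|---|---|---|
| 0.50 | 0.70/0.50 = 1.40 | 1.38 | 0.69 |
| 0.70 | 0.70/0.70 = 1.00 | 1.00 | 0.70 |
| 1.00 | 0.70/1.00 = 0.70 | 0.69 | 0.70 |
| 1.30 | 0.70/1.30 = 0.54 | 0.54 | 0.70 |

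The joint coefficient is reversed, hidden, unchanged or exaggerated, depending on a later-line effect that nobody knows in advance. The standard error of the first-line log-HR is 0.18 to 0.19 in the joint coding and about 0.147 in the three-level coding.

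**Step 3: immortal time added.** The basic set-up is the same, but a later trial is possible only for patients alive at entry and has no true effect. First-line participation is 10 to 25% and later-trial probability 20 to 30%. Indicators are ever/never.

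| True first-line HR vs none | Later-only vs none | Three-level static, first-line vs none | Joint first-line HR |
|---|---|---|---|
| 1.00 | 0.60–0.63 | 0.89–0.93 | 1.48–1.50 |
| 0.85 | 0.60–0.62 | 0.76–0.79 | 1.26–1.28 |
| 0.70 | 0.60–0.63 | 0.62–0.65 | 1.03 |

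The joint figure is again the ratio of the other two, for example 0.93/0.63 = 1.48. A later trial with no effect appears to cut the hazard by about 40%. Static three-level coding is the same fit as the joint model and remains biased. At 400 and 500 patients the joint HR for a true 0.70 is 1.04 and 1.05. With a harmful later-line HR of 1.5 it is 0.79.

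**Step 4: separating the two causes.** With no true effect anywhere, the first-line versus later-only HR is truly 1.0, so nesting alone cannot move it. Further single simulations assumed 20% trial entry per line and median OS of 18 months.
- No true effect, ever/never: 1.21, 1.26, 1.36 and 1.38 in four simulations of 3,000 to 12,000 patients.
- No true effect, later trial time-dependent: 0.99 (4,000 patients) and 0.89 to 0.92 (3,000 patients, within sampling noise of 1.0). The apparent harm goes.
- True HR 0.80 at every line, nested: 1.31 and 1.32 ever/never; 1.01 and 1.00 with the any-trial term time-dependent. Immortal time is gone, but the contrast is still first-line versus later: 0.80/0.80 = 1.00.
- Same scenario, three levels with time-dependent switching: 0.80 and 0.82.

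Only the last coding answers the intended question.

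**Step 5: imperfect nesting.** If 10% of patients are locally advanced and their first-line trial does not count as metastatic-stage, the joint HR in the step 3 setting with a true 0.70 is 0.94.

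**The case against.** The case on the other side has real substance.

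- **Joint entry is inferred.** The list names variables for several univariate and multivariate models. No sentence says that both indicators stay in one final model. This stands, but nothing prevents it either, and followed literally the plan enters both. The univariate analyses escape this problem, although a univariate first-line model mixes never-trial and later-trial patients in its reference group (0.67 to 0.81 for a true 0.70 with later status fixed).
- **Nothing is lost.** First-line versus none is bF + bA, a one-line contrast. That is true, but the plan does not specify it and a standard coefficient table does not show it. With ever/never coding the sum carries the immortal-time bias as well.
- **Nesting is not strict.** First line is undefined in the list, and an unresectable locoregional patient may enter a first-line trial before any metastasis. This stands: the cell for first-line trial without metastatic-stage trial is empty among metastatic patients only, not in the whole cohort.
- **The stakes are limited.** The primary objective is descriptive, and this concerns one pair of covariates in secondary models. This stands and bears on priority.

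A reader might infer that the coding necessarily hides or reverses a first-line benefit. Step 2 shows that it need not. A reader might also infer that nesting by itself manufactures harm, or that a three-level recode alone is enough. Steps 3 and 4 contradict both.

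**Conclusion.** The point holds in a conditional form. If first line is the first metastatic line and both indicators enter one model, the first-line coefficient among metastatic patients is a comparison with later-only trial patients. For a true HR of 0.70 versus no trial it ranges from 0.54 to 1.38 over later-line HRs of 1.30 down to 0.50.

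Separately, ever/never coding of any metastatic-stage trial brings immortal-time bias into OS from metastatic diagnosis. That bias accounts for the apparent first-line HR of about 1.2 to 1.5 when there is no effect.

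The two algebraic facts do not depend on the simulations. The sizes do, and they rest on assumed participation, survival and line timing, because the documents give none of these. The documents do not support saying that the effect will be hidden or reversed, only that it can be. The change should be made before the OS models are run; it does not touch the primary descriptive objective.

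**What to change.** 1. Define first line as the first metastatic (or palliative) line, so that unresectable locoregional patients are classified by the same rule.
2. In the Cox models for OS from metastatic or unresectable diagnosis, replace the two covariates with one three-level variable: no trial so far (reference), trial at first line, first trial at a later line. Each trial level switches on at the start date of the line concerned; until then the patient counts under no trial.
3. In the logistic model for survival 5 years after metastases, where a time-dependent term cannot enter, use first-line trial status only. Alternatively, use a landmark version: patients alive at a stated time, classified by trial entry up to it.
4. State which trial variable, if any, enters the TNT models and the logistic models for later-line treatment. These were not quantified here.

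The cost is a few sentences of SAP wording and a recode. The Variables section already collects trial inclusion with systemic treatment for metastatic disease and the start date of each line, so no new data are needed.
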